6.2. Overall Rationale for the Study

SARS-CoV-2 has spread rapidly and globally since its emergence, causing COVID-19. The World Health Organization (WHO) declared that the outbreak constituted a public health emergency of international concern on 30 January 2020 and declared the outbreak to be a pandemic on 11 March 2020. Due to the global spread of COVID-19 pandemic, rapid development of a COVID-19 vaccine is a worldwide priority.

Following the primary analysis of the Phase 3 study COV3001, the US FDA granted an EUA for the Ad26.COV2-S vaccine for use in individuals 18 years of age and older on 27 February 2021. However, following a successful efficacy analysis that supports issuance of a EUA, further evaluation of the Ad26.COV2-S vaccine is still needed, including observational studies that leverage health insurance claims databases and more precise estimation of vaccine effectiveness ([Center for Disease Control and Prevention 2020](#)). Active surveillance of vaccines through additional pharmacovigilance activities such as observational studies should also be considered.

Per communication by the European Commission on October 15, 2020 ([European Commission 2020](#)), the Commission has entered into agreements with individual vaccine producers on behalf of the Member States, purchasing and/or reserving the right to purchase vaccine doses under Advance Purchase Agreements ([European Union 2020](#)). Member States and public health authorities should prepare to undertake studies of vaccine effectiveness and safety via coordination by the EMA and the European Centre for Disease Prevention and Control (ECDC), and specifically to prepare for participation in large-scale EU-wide effectiveness and safety monitoring studies.

To fulfil its regulatory obligations, the sponsor plans to initiate a post-authorisation safety study (PASS) aiming to characterise and evaluate the safety profile of Ad26.COV2.S in a large population sample size and to inform the scientific community on AESIs that could be associated with the use of Ad26.COV2.S.

7. RESEARCH QUESTION AND OBJECTIVES

Research Question

This study has 2 chronologically consecutive aims: 1) to conduct a feasibility assessment aiming to inform the safety evaluation study and 2) to assess the risk of developing pre-specified and newly identified AESIs following administration of Ad26.COV2.S.

Objectives

Feasibility Assessment

The feasibility assessment will include the following objectives (not all objectives may be assessed in all analyses):

- To provide a comprehensive overview of the methods for identification of COVID-19 vaccine exposure including provenance of data and linkage to vaccination registry
- To monitor the number of individuals exposed to any COVID-19 vaccines (Ad26.COV2.S, Vaxzervria vaccine and mRNA COVID-19 vaccines) and to investigate the risk of misidentification of the COVID-19 vaccine exposure. Both missing vaccination instances and misclassification of the type of vaccine will be assessed with the benchmark provided by the ECDC: <https://vaccinetracker.ecdc.europa.eu/public/extensions/COVID-19/vaccine-tracker.html#uptake-tab>)
- To compare individuals receiving different COVID-19 vaccines with respect to demographics and clinical characteristics of recipients, potential confounders and risk factors for the AESI
- To conduct time-to-onset analyses for the sponsor prioritised AESIs (including exacerbation of asthma) with respect to time since vaccination and without prespecified risk windows
- To describe booster vaccine doses in individuals who received a first dose of Ad26.COV2.S.

The joint evaluation of the objectives mentioned above will inform on the overall feasibility of the study.

Safety Evaluation Study

Primary objective

The primary objective of this safety evaluation study is to assess the potential association between the occurrence of predefined and newly identified AESIs and vaccination with Ad26.COV2.S compared to individuals unexposed to any COVID-19 vaccine, and to individuals exposed to other types of COVID-19 vaccines (mRNA or adenovirus platforms) within disease-specific risk periods, and among the vaccinated, to a control window within the same individual.

Secondary objectives

The secondary objectives of this study are to assess the potential association between the occurrence of predefined and newly identified AESIs and vaccination with Ad26.COV2.S in the following specific subpopulations (part of the main study population):

-
- Immunocompromised individuals,
 - Pregnant women,
 - Individuals who have a prior history of thrombotic events and/or thrombocytopenia,
 - Prior COVID-19 infection,
 - Individuals with a prior history (ever) of the specific event more than a year before start of follow-up.

These results will be compared to COVID-19 vaccine unexposed individuals and, to individuals exposed to other types of COVID-19 vaccines (mRNA or adenovirus-based platforms) or compared to a control window within the same individual.

Endpoints

Feasibility Assessment

The endpoints for the feasibility assessment, including a monitoring phase, are:

- Quality assessment of data that has been extracted from the source data banks (completeness, logic and benchmarking between data sources and against external data)
- The number of doses and uptake of different COVID-19 vaccines by calendar time
- The demographic and morbidity characteristics of individuals receiving the different COVID-19 vaccines
- Algorithms for AESI identification (including exacerbation of asthma)
- Incident rates and cumulative incidence (risk) of the selected AESIs and corresponding 95% confidence intervals (CIs), without prespecified risk windows
- Risk factors for AESI.

Safety Evaluation Study

The primary endpoints for the safety evaluation study are to estimate the risk of the selected AESIs listed below among individuals vaccinated with the Ad26.COV2.S vaccine and in corresponding unexposed individuals and individuals exposed to other types of COVID-19 vaccines (split between mRNA platform-based vaccines and adenovirus-based platforms), or during a control window within the same individual.

The contractual agreements with data partners will stipulate the ability to allow newly identified AESIs to be incorporated into the study objectives, and the current protocol that will be used for governance approvals will state that additional AESI may be added. Each data access provider is responsible to inform the appropriate ethics boards of these amendments.

Acute events (events expected to be recorded within 60 days of vaccination).

- The incidence of anaphylaxis within 0-2 days.

- The incidence of generalized convulsion, arrhythmia, acute kidney failure and acute hepatic failure within 1-14 days.
- The incidence of the following events within 1-28 days
 - thrombotic events (microangiopathy including capillary leak syndrome), disseminated intravascular coagulation, deep vein thrombosis, pulmonary embolism, cerebral vein thrombosis, peripheral thrombosis, thrombosis with thrombocytopenia and ischemic strokes, acute coronary syndrome (acute myocardial infarction, unstable angina, and new onset angina),
 - bleeding events including haemorrhagic stroke (no subarachnoid),
 - composite endpoint: Venous thrombosis (including pulmonary embolism and deep vein thrombosis)
 - composite endpoint: Arterial thrombosis (including acute coronary syndrome and ischemic stroke),
 - composite endpoint: stroke (including haemorrhagic and non-hemorrhagic stroke)
 - heart failure, and stress cardiomyopathy.
- The incidence of immune/inflammatory events: encephalitis (including acute demyelinating encephalomyelopathy and meningoencephalitis), Guillain-Barré Syndrome, Bell's palsy, immune thrombocytopenia, thrombocytopenia, transverse myelitis and cardiac inflammatory disorders (including myocarditis and pericarditis) within 1-42 days.
- The incidence of sensorineural hearing loss within 1-60 days.
- The incidence of asthma exacerbation within 1-14 days.

Non-acute events (events expected to be recorded >60 days after vaccination)

- The incidence of new-onset autoimmune thyroiditis, multiple sclerosis, acute aseptic arthritis, and type 1 diabetes mellitus within 1-365 days.

Newly identified AESI may be incorporated into the list of AESI to be investigated by the current study if a safety signal occurs.

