To fulfil the regulatory obligations, the sponsor plans to initiate a Post-Authorisation Safety Study (PASS) aiming to characterise and evaluate the safety profile of Ad26.COV2.S in a large population sample size and to inform the scientific community on AESIs that could be associated with the use of Ad26.COV2.S.

Research Question and Objectives

This study has two chronologically consecutive aims: 1) to conduct a feasibility assessment aiming to inform the safety evaluation study and 2) to assess the risk of developing pre-specified and newly identified AESIs following administration of Ad26.COV2.S vaccine.

Objectives

Feasibility Assessment

The feasibility assessment will include the following objectives (not all objectives may be assessed in all analyses):

- To provide a comprehensive overview of the methods for identification of COVID-19 vaccine exposure including provenance of data and linkage to vaccination registry

- To monitor the number of individuals exposed to any COVID-19 vaccine in each database and to investigate the risk of exposure misidentification. Both missing vaccination instances and misclassification of the type of vaccine will be assessed using the benchmark provided by the ECDC: <https://vaccinetracker.ecdc.europa.eu/public/extensions/COVID-19/vaccine-tracker.html#uptake-tab>)
- To compare individuals receiving different COVID-19 vaccines concerning demographics, clinical characteristics of recipients, potential confounders, and risk factors for the AESI
- To conduct time-to-onset analyses for the AESIs (including exacerbation of asthma) concerning time since vaccination without prespecified risk windows.
- To describe booster vaccine doses in individuals who received a first dose of Ad26.COV2.S vaccine.

Safety Evaluation Study

Primary objective

The primary objective of this safety evaluation study is to assess the potential association between the occurrence of predefined and newly identified AESIs and vaccination with Ad26.COV2.S compared to individuals unexposed to any COVID-19 vaccine, and to individuals exposed to other types of COVID-19 vaccines (mRNA or adenovirus platforms) within disease-specific risk periods, and among the vaccinated, to a control window within the same individual.

Secondary objectives

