8.1.2. Overview of Study Design for Safety Evaluation Study

Evaluation of safety concerns will be conducted using a retrospective observational study in electronic health care databases of various types in Europe. Eligible individuals will be included in the study from the start of Ad26.COV2.S vaccination in each participating country, and the study will end at the last date of data availability in each database.

For each AESI, the study design of the safety evaluation study will depend on whether the AESI is an acute or non-acute event and follow the decision framework described in the ACCESS template protocols for evaluation of safety events in electronic health care databases ([Dodd 2020](#)).

The primary study design for the evaluation of acute events (events expected to occur within 2, 14, 28, 42, or 60 days of vaccination) will be a self-controlled risk interval (SCRI) design with pre- and post-vaccination control window and for non-acute events (events expected to occur within 365 days) will be a cohort design with concurrent unexposed comparators. Additionally, the cohort analysis will also include two active comparator groups: one viral vector vaccine comparator group (i.e., Vaxzevria[®] [AZD1222] by Oxford/AstraZeneca) and one mRNA vaccine comparator group (i.e., Comirnaty[®] [tozinameran] by Pfizer/BioNTech and/or Spikevax[®] [elasomeran] by Moderna), where possible (pending on the feasibility analysis with a maximum follow-up time of one year).

In sensitivity analyses, an equivalent cohort design will also be used to assess acute events. When it is established that data sources do not capture vaccinations well during the feasibility assessment, we will conduct a sensitivity analysis excluding these data sources from the cohort analysis with non-exposed comparators for the non-acute events, to avoid misclassification of exposure.

Another sensitivity analysis will compare the Ad26.COV2.S vaccine with active comparators (1) a 1-dose strategy and (2) a 2-dose strategy.

Individuals start follow-up at the start of each risk window and end follow-up at the earliest occurrence of latest data availability of the databank, individual exit from the database, completion of the study period, or death. At least one year of enrolment prior to the index date (date of vaccination) will be required to determine whether individuals meet the study criteria and to define baseline characteristics. If more historical data is available, this will be included.

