8.3. Variables

8.3.1. Exposure Assessment

Exposure will be based on available prescriptions, dispensing, or administration of the Ad26.COVS.S and other COVID-19 vaccines. Vaccine receipt and date of vaccination will be obtained from all possible sources that capture COVID-19 vaccination, such as pharmacy dispensing records, general practice records, immunisation registers, vaccination records, medical records, or other data banks. During the feasibility assessment, the completeness of information will be assessed and described. Depending on the data source, vaccines may be identified via nationally used product codes (including batch numbers) where possible. The exposure of interest for the safety evaluation study is the receipt of Ad26.COVS.S vaccine.

- SIDIAP (ES): SIDIAP will have available information on the administration of COVID-19 vaccines to individuals linked to a unique and anonymous identifier. The information will be originated from the electronic medical records. For each patient, SIDIAP will have the date and centre of administration, health professional administering the vaccine, dose, brand, reasons for vaccination (e.g., risk group), and other information related to vaccination.
- VID (ES): For the inhabitants of the Valencia region, FISABIO will capture all COVID-19 vaccines through the immunisation register. The Vaccine Information System includes administration dates, brand and batch from each dose.
- PHARMO DATABASE NETWORK (NL): Data on vaccination will be obtained from PHARMO's general practitioners' GP database. Information on vaccines includes brand, batch, and date of administration/recording. Several COVID-19 vaccines have been administered outside traditional medical care settings and linkage with a GP database is not yet implemented, this may change over time.
- ARS Toscana (IT): ARS will identify vaccines from the regional immunisation register using the nationally used product code, including batch number. See section [8.2.1](#) regarding conditional participation of ARS Toscana.

The vaccination strategies for the different exposure groups will be defined as follows:

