8.7.1.1. Feasibility Analysis

Demographic and Baseline Characteristics

The distributions of baseline characteristics at start of COVID-19 vaccination for each COVID-19 vaccine exposure group will be calculated to describe differences between the groups. For continuous variables, means, standard deviations, medians, and other quartiles will be estimated. For categorical variables, counts and proportions will be estimated. The missingness of variables will also be described.

Vaccine uptake

For every data source, the number of administered doses per COVID-19 vaccine brand within the primary series (dose 1 and dose 2) will be calculated by calendar time (in months) over the follow-up period.

For individuals with a given year of birth vaccination uptake for dose 1 over time will be calculated. The coverage at month i for birth year j is calculated by dividing the number of vaccinated individuals n_{ij} by the total number of individuals under follow-up at month i (N_{ij}), expressed as a percentage. Estimates of vaccination uptake will be compared with data provided by ECDC.

Algorithms for outcome definitions

For each outcome, the number of cases by diagnosis code will be counted, and the impact on the case count will be assessed when confirmatory medications /procedures or laboratory tests are used. All such counts will be stratified by meaning (GP record, hospitalisation primary diagnosis, hospitalisation secondary diagnosis).

Time-to-onset

Descriptive analyses of the time-to-onset of event (up to one year after vaccination) may inform the selection of risk intervals for the sensitivity analyses.

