8.9. Limitations of the Research Methods

This study is subject to limitations related to both the study design and the use of secondary healthcare data.

Design

A list of AESI was defined based on Safety Platform for Emergency vACCines (SPEAC) work and additional safety concerns that were raised by the FDA/CDC in the US and EMA in the EU around cases of TTS. The SPEAC list includes a large range of events considered as potential risks that may occur after the administration of a COVID-19 vaccine. The listed AESIs are potentially related to vaccine platforms, natural COVID-19 development, or raised with other marketed vaccines. This study protocol will include all events that are considered as identified risks or risks potentially related to the Ad26.COVS.S vaccine, some of which events were also added as they were observed during the Phase 3 study VAC31518COV3001 and in the US or Europe during the post-authorisation use. Over the 12-month period between vaccine launch and study implementation, the list of AESIs may be amended based on available evidence on the safety profile of the Ad26.COVS.S vaccine.

Given the broad list of potential events that could be associated with the Ad26.COVS.S vaccine and the large heterogeneity in the type of events, acute versus long latency diseases, different study design approaches will be used depending on the type of event. For acute events, the primary study design will be the SCRI design (Baker 2015), which is preferred due to its inherent control for time-constant factors; additionally, because it is restricted to vaccinated individuals, it avoids bias due to misclassification of unexposed individuals due to vaccination outside of traditional medical care settings, which may not be captured the data bank.

Data

Data-related limitations of this study are the reliance on the secondary use of data that has been collected for other purposes. Outcomes and their dates of occurrence will be validated, but the extent of validation may be limited because of the use of medical records. Furthermore, it is unknown the extent to which vaccine brands and batch numbers/lot numbers will be available in the secondary data sources.

Misclassification of COVID-19 vaccination

The COVID-19 vaccines have been rolled out quickly and in special circumstances because of cold-chain requirements and specific risk group channelling. In many healthcare systems,

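### ECDC uptake totals can show a net surplus or deficit per brand but cannot measure misclassification of vaccine type, the purpose the protocol gives them

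*Protocol*

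**What the plan says.** The feasibility objectives in Section 7 include investigating the risk that COVID-19 vaccine exposure is misidentified. Two errors are named and one method is given for both: "Both missing vaccination instances and misclassification of the type of vaccine will be assessed with the benchmark provided by the ECDC". The Abstract says the same: "Both missing vaccination instances and misclassification of the type of vaccine will be assessed using the benchmark provided by the ECDC".

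Section 8.7.1.1 describes the quantities, and all are totals:
- Doses: "For every data source, the number of administered doses per COVID-19 vaccine brand within the primary series" is counted by calendar month.
- Coverage: "For individuals with a given year of birth vaccination uptake for dose 1 over time will be calculated". The formula is indexed by month and birth year, with no index for brand.
- Comparison: "Estimates of vaccination uptake will be compared with data provided by ECDC".

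Section 8.3.1 lists record-level fields. For VID, "The Vaccine Information System includes administration dates, brand and batch from each dose". PHARMO holds brand, batch and date; SIDIAP holds brand, dose and date. ARS Toscana would have product code and batch, but Section 8.2.1 says it cannot contribute data at present. Section 8.9 cautions that "it is unknown the extent to which vaccine brands and batch numbers/lot numbers will be available in the secondary data sources".

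Section 8.9 also says that incomplete vaccination records do not threaten the internal validity of the SCRI, because it includes only Ad26.COV2.S recipients.

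**The concern.** Vaccine type defines the exposed group in every primary analysis. It also separates the groups in both active-comparator cohorts. The question for each source is what proportion of people recorded as Ad26.COV2.S recipients actually received it. A comparison of totals does not answer that, because errors in opposite directions cancel and missing doses can hide wrong-brand doses. On a strict reading of Section 8.7.1.1, the coverage estimate set against ECDC carries no brand at all. On a generous reading, the per-brand monthly counts are compared too, and they show only the net error.

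No other passage ties a check to recorded vaccine type. Case validation in Section 8.3.3.1 concerns outcomes. The exposure sensitivity analysis (Sections 8.1.2, 8.1.3, 8.7.6 and 8.9) deals with vaccinated people counted as unexposed. Item 5.2 of the ENCePP checklist in Annex 1, on validity of exposure measurement, is answered No. The reassurance about the SCRI in Section 8.9 holds only if the recorded brand is right. At stake is dilution of the Ad26.COV2.S estimates that a match with ECDC would not reveal.

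**Working it through.** The protocol gives no figure for vaccine-type error, so there is none to reproduce.

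**Inputs**
- Source population 18.1 million, with up to 10% vaccinated with Ad26.COV2.S (Section 8.5): A = 0.10 × 18.1 = 1.81 million.
- Assumed: 50% to 80% of the source population has had some COVID-19 vaccine. Recipients of other vaccines: O = (0.50 − 0.10) × 18.1 = 7.24 million to (0.80 − 0.10) × 18.1 = 12.67 million.
- Assumed: f, the share of O recorded as Ad26.COV2.S. Let g be the share of A recorded as another vaccine, and m the share of A not recorded at all.

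**Step 1: what the total identifies**

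Recorded Ad26.COV2.S = A(1 − g − m) + fO. This equals A whenever (g + m)A = fO. One total cannot determine three unknowns, and g and m enter only as their sum, so wrong-brand and missing doses cannot be told apart. When the total matches, the wrong share among recorded recipients is w = fO/A.

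**Step 2: size when the total matches exactly**

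Observed IRR = (1 − w) × 3 + w × 1, for a true IRR of 3 and no excess risk from the other vaccine.

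| f (assumed) | Wrong records, fO | w, also the g + m needed | Observed IRR |
|---|---|---|---|
| 0.5% | 36,200 to 63,350 | 2.0% to 3.5% | 2.96 to 2.93 |
| 1% | 72,400 to 126,700 | 4% to 7% | 2.92 to 2.86 |
| 2% | 144,800 to 253,400 | 8% to 14% | 2.84 to 2.72 |

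In every row the recorded count is 1,810,000 and the difference from the benchmark is zero.

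**Step 3: a lower share**

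If 5% of the source population had Ad26.COV2.S (assumed), f = 1% gives w = 0.45 × 1% / 5% = 9% to 0.75 × 1% / 5% = 15%. The observed IRR is 1 + 2 × 0.91 = 2.82 to 1 + 2 × 0.85 = 2.70.

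**Step 4: SCRI power**

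Power = Φ[(√n |p − 0.5| − 1.96 × 0.5) / √(p(1 − p))], with p = RR/(1 + RR). For n = 69 and RR 2 this gives 80.5%, as in Table 4. At w = 4% and 7%, RR 2 becomes 1.96 and 1.93, and power falls to 78.1% and 76.2%.

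**Step 5: what the benchmark can detect**

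With f = g = 1% and m = 0, the net surplus is fO/A − g = 4% − 1% = 3% to 7% − 1% = 6%. A brand-level comparison could show this.

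**Step 6: direction**

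In general, observed RR = (1 − w)RR₁ + w·RR₂, where RR₂ belongs to the vaccine actually received. If RR₂ exceeds RR₁, the estimate rises. Section 6.1 reports similar cases of thrombosis with thrombocytopenia after the AstraZeneca vaccine, so no excess risk cannot be assumed for every AESI.

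**The case against.** The strongest reply has four parts.

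- **Cancellation takes a particular error pattern.** A match at f = 1% needs 4-7% of true Ad26.COV2.S doses to be misrecorded or missing. Equal error rates in both directions would leave a surplus, and the monthly counts mean that cancellation would have to recur. This stands as a limit on likelihood. It does not make a total a measure of record-level error, and missing doses alone can supply the offset.
- **Other checks exist.** Section 7 lists completeness, logic and benchmarking checks. Section 8.6.2 has Level 1 to 3 checks, and Section 8.8.5 has logic checks in SIDIAP. A brand check could sit there, but none of these is tied to vaccine type.
- **Detail belongs in the SAP.** The particular consistency rules do. The point here is that the protocol itself names a method that cannot meet its stated objective.
- **Brand and batch availability is called unknown.** That limits the remedy in some sources.

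A reader might infer that this check decides which data enter every analysis, so that a false pass contaminates them all. The documents do not support that. The rule that starts "When it is established that data sources do not capture vaccinations well during the feasibility assessment" leads only to a sensitivity analysis in the cohort with non-exposed comparators. It does not gate the SCRI or the active-comparator cohorts.

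**Conclusion.** The point holds as one of measurement. ECDC totals can reveal a net discrepancy. They cannot give the proportion of recorded Ad26.COV2.S recipients who truly received it, or separate wrong brand from missing doses. This follows from the algebra and the protocol's own description, without any outside figure.

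The size is unknown. Under the stated assumptions (10% ceiling, 50-80% vaccinated, 1% of other recipients recorded as Ad26.COV2.S, total still matching), 4-7% of recorded recipients are wrong. A true IRR of 3 then reads about 2.9 if the other vaccine carries no excess risk. Smaller Ad26.COV2.S shares give more dilution, and the direction may differ by AESI.

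A reader might also infer that a fifth or a third of recorded recipients are wrong, by taking Ad26.COV2.S as 5% or 3% of vaccinees: 0.95 × 1% / 5% = 19%, and 0.97 × 1% / 3% = 32%. The documents do not support this. The 10% in Section 8.5 is of the whole source population, which is 20% to 12.5% of vaccinees if 50-80% are vaccinated. An exact match at those lower shares would need 19% or 32% of true Ad26.COV2.S doses to be misrecorded or missing. Equal 1% errors would instead show as a surplus of about 18% or 31%.

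**What to change.** - In Section 7 and the Abstract, limit the ECDC comparison to total uptake and net uptake per brand.
- State that vaccine type will be assessed at record level in each source with the fields available: agreement of brand with batch where batch is recorded, different brands recorded for one person on one date, and implausible dose sequences.
- Report the discordance rates for each source before the final analysis.
- Repeat the SCRI and cohort analyses without discordant records as a sensitivity analysis.
- In Section 8.9, make the statement about the SCRI conditional on the recorded brand being correct.

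The cost is a few changed sentences, the consistency rules in the SAP and a short check on brand, batch and dose fields. Batch is not available in every source, so the check will be weaker in some. A few records are lost in the sensitivity analysis. Consistency checks will also miss errors where brand and batch are wrong together, so the discordance rate indicates the error rate but does not measure it fully.
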